We will measure child behavior problems using the Eyberg Child Behavior Inventory (ECBI).⁸¹ The ECBI is a 36-item scale designed to measure the presence and intensity of problem behavior. Each item is measured on two scales: the Problem Scale (dichotomous) and Intensity Scale (7-point). The ECBI is a valid measure of child behavior problems, with established convergent validity across racial and ethnic populations and economically and linguistically diverse samples.⁸¹⁻⁸³ Cronbach's alpha reliabilities of the Intensity and Problem Scale scores are .92 and .99.²⁴ In addition, the Strengths and Difficulties Questionnaire (SDQ) will provide a measure of child behavior problems and prosocial behavior. The 25-item SDQ has a five-factor structure (emotional, conduct, hyperactivity-inattention, peer, and prosocial) using a 3-point scale. Mean Cronbach's alpha for the SDQ is .73.⁸⁴ The SDQ has been validated in multiple cultures and socioeconomic levels.⁸⁵

Aim 2: Cost effectiveness analysis. Data for the cost effectiveness analyses will be drawn from invoices, staff report, study records, EHR, and eCPP electronic time stamps (Table 4). Resources used for the

Table 4. Description of Resource and Cost Measures

Cost Category	Source	Unit of Measure	Translation to Costs
eCPP costs			
eCPP delivery costs	Invoice	Participant	Average cost/participant
Orientation delivery costs			
EHR modification	Programmer report	Minutes/site	Programmer average hourly wage
Clinician time receiving study orientation	Study records	# of clinicians Minutes/clinician	Clinician average hourly wage
Time to lead orientation	Study records	Minutes	Study staff average hourly wage
Clinician costs			
Time to introduce study*	EHR	Minutes/ participant	Clinician average hourly wage
Parent costs			
Time spent learning about the study*	EHR	Minutes/ participant	Parent average hourly wage
Time spent completing eCPP modules	digital time logs	Minutes/ participant	Participant average hourly wage

EHR = Electronic Health Record; *time for introducing and learning about the study includes all parents (non-participants and participants), averaged across the # of participants.

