intervention include the eCPP costs (e.g., tablet, tech support, and maintenance costs), modification of the EHR, orientation for clinicians, and time for the clinician to introduce the study to parents during well-child visits. Participant costs are primarily the parents' opportunity costs, representing the value of their time spent in the intervention or control condition, respectively. Participant costs include time spent completing the eCPP. Resources used will be translated into costs by multiplying the number of units with the cost per unit for each cost category.

Aim 3: RE-AIM data collection. Process tracking forms will be created to record the evaluation data, if not already part of the RCT outcome data (Table 5). These data will be collected monthly by study staff at each site during the recruitment phase from the 4 primary care practice sites, clinicians, and participants.

Table 5. Data and Source for RE-AIM Evaluation

RE-AIM component	Data and Source
REACH: Proportion and characteristics of parents from the practices that were introduced to and enrolled in the study.	# of monthly well-child visits for children aged 2-5 over course of study recruitment (source: EHR) # of parents who were introduced to the study during a well-child visit (source: EHR) # of parents who enrolled in the study (consented/randomized) # of parents who were not introduced to the study and reason (source: EHR) Characteristics of parents enrolled in the study (source: demographics [C.5.a], Technology Inventory ^a)
EFFICACY: Evaluation of intervention efficacy.	Efficacy of the eCPP intervention is assessed as part of the RCT arm of the study by changes in parenting and child behavior. [Specific Aim 1- RCT (Hypothesis 1a)]
ADOPTION: Characteristics of clinicians and practices oriented and agreeing to deliver the intervention (e.g., introduce the study to eligible parents).	Clinician characteristics: MD or NP, specialty, years in practice, and current practices of managing parenting and child behavior concerns (source: Primary Clinician Survey ^b). Site characteristics: # of patients aged 2-5, average time of well-child visits (source: EHR). # of orientation sessions per practice site and proportion of clinicians that attend the orientation (source: attendance records).

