All analyses for Aim 1 will be performed on an intent-to-treat basis. As multiple dependent variables are being examined, a repeated-measures multivariate analysis of variance (assessment x intervention condition) will be conducted to ensure control of experiment-wise Type-I error, and to perform an initial assessment of intervention effects. We will then test intervention efficacy using multilevel growth models⁹⁰⁻⁹² with three levels (assessments [Level 1] within parent [Level 2] within primary care practice site [Level 3]). Intervention condition will be dummy coded (eCPP vs. control) at Level 2, and covariates at site-level (e.g., clinic size) or parent-level (e.g., age, race/ethnicity) will be included at the appropriate level of analysis. By including baseline measures of the outcome variable being tested as a covariate at Level 2 (parent level) and setting the intercept at the 3-month assessment, we will be able to test Hypothesis 1A (intervention effects between baseline and 3-month assessment) as the main effect of intervention condition (i.e., controlling for baseline level of the outcome being tested). The condition x time interaction will then serve to test differential change in outcome measures following the 3 months of active intervention, and planned contrasts will be estimated to test Hypothesis 1B (maintenance of intervention effects at 6 and 12 months).

Aim 2. Compare the cost-effectiveness of the eCPP intervention relative to control for parenting and child outcomes. **HYPOTHESIS 2:** The eCPP is cost-effective relative to control for parenting and child outcomes.

We will assess cost-effectiveness of eCPP from the societal perspective, including costs borne by the program, health care system, and parent. We will conduct additional analyses from the program, health care system, and parent perspectives separately. For the cost measurement, quantities of resources used and their associated prices will be collected for the eCPP (either prices paid or value of the clinician time) and participant (i.e., value of participant's time to use the eCPP). Program and parent costs will be calculated for the 12-month study duration and summed to calculate total cost per parent. All costs will be valued in 2015 dollars.

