For the effectiveness measurement, effectiveness will be measured using the parenting and child outcomes. Cost-effectiveness will be evaluated by combining the mean total cost per parent with effectiveness (parenting and child behavior outcomes). We will calculate the incremental cost-effectiveness ratio (ICER) for eCPP compared to the control condition, such that $ICER = (C_1 - C_0)/(E_1 - E_0)$, where C is cost and E is effectiveness. Subscript 1 denotes eCPP and subscript 0 denotes the control condition; 95% confidence intervals for the ICERs will be calculated to evaluate the uncertainty in these results.⁹³⁻⁹⁵ We will conduct one-way and multi-way sensitivity analyses for the key parameters to evaluate whether the ICERs are sensitive to plausible changes in their values. The sensitivity analysis is a check on the robustness and will determine the key parameters impacting the ICERs. We will also plot acceptability curves based on varying threshold (willingness to pay) values for adherence and change in parenting and child behavior outcomes.

Aim 3. Quantify the levels of program implementation of eCPP in primary care using the RE-AIM framework. **RESEARCH QUESTION 3:** What is the degree of Reach, Efficacy, Adoption, Implementation, and Maintenance of the eCPP intervention in pediatric primary care?

Descriptive statistics will be calculated to identify achievements across each level of RE-AIM for each primary care site. We will develop a demographic, income, and technology use profile for the populations reached (i.e., parents enrolled in the study). We will use contingency table analyses and independent *t* tests to compare the demographic and income profiles to the characteristics of the population of the primary care sites service catchment communities using data from the U.S. Census. This analysis will allow us to assess the extent to which we are either over- or under-representing our priority populations (low-income families) from the local catchment area in this study. Technology ownership and use will be compared to data from national data sets from the Pew Research Center's Internet and American Life Project.⁹⁶

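### Aim 2 counts the value of parents' time in the control condition, but names no measure or source for that time

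*Combined protocol and SAP*

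**What the plan says.** Three parts of the document bear on control-arm cost.

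- **Definition of cost.** Under Measures, Aim 2, participant costs are mainly parents' opportunity costs, "representing the value of their time spent in the intervention or control condition, respectively". The next sentence itemises only one arm: "Participant costs include time spent completing the eCPP".
- **Sources and units.** The same section says: "Data for the cost effectiveness analyses will be drawn from invoices, staff report, study records, EHR, and eCPP electronic time stamps". Table 4 has one parent row for time after randomization, "Time spent completing eCPP modules", taken from digital time logs in minutes per participant and valued at "Participant average hourly wage". Its starred rows take study-introduction time from the EHR; the footnote says this covers all parents and is averaged over participants.
- **Analysis.** In the analytic plan for Aim 2, "quantities of resources used and their associated prices will be collected for the eCPP", and the participant side is glossed as the "value of participant's time to use the eCPP". Then: "We will calculate the incremental cost-effectiveness ratio (ICER) for eCPP compared to the control condition", with the formula (C1 - C0)/(E1 - E0). The main perspective is societal, with separate program, health care system and parent analyses over 12 months.

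Under Study Design, control parents receive tablet-based materials of the kind their practice would normally give, and have access to them over the intervention period.

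**The concern.** The plan defines control parents' time as a cost and subtracts a control cost, but each place that says how usage time will be obtained refers to the eCPP alone. An analyst following those rules would have nothing to enter for time spent in the control condition. C0 would omit it and C1 - C0 would be misstated.

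Hypothesis 2 rests on that difference. If eCPP is both more effective and more costly, an overstated increment raises the ICER and works against the hypothesis. The parent-perspective analysis is most exposed because parent costs are mainly time. The planned sensitivity analyses could vary an assumed control time, but no measured value would anchor the range, and variation between parents in that cost could not enter the confidence interval for the ICER. Usage that is not logged during the trial cannot be recovered objectively afterwards.

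**Working it through.** The plan states no cost, wage, minutes or value of C0, so there is no figure to reproduce. The check matches each time item to the arm it covers and then does the algebra.

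**Coverage of parent time**

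| Item | Place | Arm covered |
|---|---|---|
| Opportunity cost of time, as defined | Measures, Aim 2 | Both |
| Electronic time stamps | Measures, Aim 2, source list | eCPP |
| Module time, digital logs | Table 4 | eCPP |
| Time learning about the study (starred, EHR) | Table 4 and footnote | All parents, at introduction only |
| Participant time | Analytic plan, Aim 2 | eCPP |
| Time on control materials | No row, source or unit | None |

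**Effect on the parent-perspective increment**

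Let w be a common hourly wage, h1 the eCPP module time, h0 control parents' time on the control materials, u1 eCPP parents' time on the same usual materials, and hi the introduction time, charged equally to both arms. Put f = h0/h1 and e = u1/h1. Both ratios are assumptions.

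1. Increment as the plan would compute it: w(h1 + hi) - w·hi = w·h1. The introduction time cancels, so the starred rows do not fill the gap.
2. Increment with all usage time counted: w(h1 + u1 + hi) - w(h0 + hi) = w·h1(1 + e - f).
3. Money misstatement: w(h0 - u1).
4. Ratio of line 1 to line 2: 1/(1 + e - f).

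| f | e | Factor |
|---|---|---|
| 0 | 0 | 1/1 = 1.00 |
| 0.10 | 0 | 1/0.90 = 1.11 |
| 0.25 | 0 | 1/0.75 = 1.33 |
| 0.10 | 0.10 | 1/1.00 = 1.00 |
| 0.25 | 0.25 | 1/1.00 = 1.00 |

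**Measuring the control arm only**

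If e = f, the true increment is w·h1. Counting material time in C0 alone would give w·h1(1 - f), which is 10% too low at f = 0.10 and 25% too low at f = 0.25. That error favours Hypothesis 2, so any measurement has to be the same in both arms.

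**Societal perspective**

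The money misstatement is still w(h0 - u1), but the increment also contains eCPP program costs. To the extent that these add to C1 - C0, the proportional effect is smaller.

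**The case against.** The strongest reply is that the control materials are usual care. Parents in both arms may use them, in which case their time cancels and omitting it does no harm. This stands as a limit on size: nothing in the document says that eCPP parents stop receiving usual materials, and at e = f the factor is 1.00. It does not settle the matter, because the plan nowhere says that control time is taken as zero or as common to both arms, and its own definition counts that time.

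Other points on that side also carry weight.

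- A reader might infer that no control-parent time is measured at all. That goes too far: the starred EHR rows include control parents' introduction time. What is missing is time spent in the control condition.
- A reader might infer that introduction time, tablets and delivery of materials are wrongly allocated. The document does not support that. The footnote's average over participants suggests an equal charge, although the text lists clinician introduction time among intervention resources. Tablets and technical support are listed as eCPP costs. These choices can be defended and need only be stated.
- The itemising sentence says what costs include and need not be exhaustive. The source list, Table 4 and the cost-measurement sentence nevertheless add nothing for control use. The usage metrics under Study Design serve the evaluation of eCPP implementation, and Table 5 lists none for control use.
- Table 1, cited under Study Design, is not in the available text and may describe control delivery. It would not alter the eCPP-only wording of the collection rules.
- No fixed cost-effectiveness threshold is set, so no decision can be shown to change.

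**Conclusion.** The concern holds in a limited form. The plan's definition of participant cost covers time in both conditions, while its collection rules cover usage time for the eCPP only. Followed as written, C0 omits control-condition time, and C1 - C0 is overstated by w(h0 - u1) whenever control parents spend more time on the usual materials than eCPP parents do.

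The size cannot be derived from the documents and may be near zero. The parent-perspective factors of 1.11 and 1.33 rest on assumed f of 0.10 and 0.25, e = 0, a common wage and equal charging of introduction time. It would be tempting to read them as the inflation to expect, or to conclude that Hypothesis 2 is bound to be penalised. The documents support neither reading, since they give no usage times and do not say whether eCPP parents also use the usual materials. The gap still deserves correction, because it is a conflict within the plan and is best closed while data are being collected.

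**What to change.** 1. Add a Table 4 row for time spent using the tablet-based usual-care or control materials: digital time logs, minutes per participant, valued at the wage used for the module row. Measure it the same way in both arms wherever parents have access to the materials, and over the same costing period.
2. Extend the Aim 2 source list to time stamps for these materials, and reword the cost-measurement sentence in the analytic plan so that participant time is collected for both conditions.
3. If automatic logging is not possible, use a self-report item in both arms at the existing 3-, 6- and 12-month assessments. Alternatively, state and justify a zero control time cost, reconcile the definition of participant costs with it, and vary it in the planned sensitivity analyses.
4. Add a clarifying sentence on how introduction time and the delivery of tablets and materials are allocated between arms.

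The cost is one table row, one usage log or self-report item, and a few edited sentences. The downside is slightly more usage data to process and, with self-report, a small added burden and recall error.

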Study Design. The study will be a person-randomized clinical trial comparing the effects of the eCPP tablet-based intervention to an enhanced usual care control condition (Table 1). Parents ($n = 312$) of 2- to 5-year-old children will be recruited from 4 primary care practices and randomly assigned to either the eCPP or control condition. Randomization will occur within sites at the participant level. Intervention parents ($n = 156$) will complete the 6 modules of the eCPP over a period of 3 months (~2 weeks/module; intervention phase) with ongoing access to the program (reference phase) throughout the remainder of the study period. Control condition parents ($n = 156$) will receive tablet-based parenting materials that they would normally receive at their primary care practice (e.g., information regarding nutrition, immunization, and exercise) and have access to the materials over the same intervention time period. Data collection in both conditions will occur at baseline and at 3, 6, and 12 months post-baseline. A descriptive design will be used to evaluate implementation of the eCPP from the perspective of practice sites, clinicians, and parents. Guided by the RE-AIM framework, we will use surveys, electronic health records, data usage metrics, and post-implementation assessments to evaluate the implementation process over the study period.

Measures.

Aim 1: Randomized Control Trial. All measures are written at the 5th grade reading level and administered on an Android tablet as computer assisted, self-interviews (CASIs). An audio option (audio-CASI) is available if parents prefer to listen to the questions. All control and outcome data are obtained by parent self-report and will be collected at each of the 4 data collection time points (baseline, 3, 6, and 12 months post baseline). Previous findings from RCTs of the group-based CPP have found significant findings across three sources of data: parent self-report, teacher report and parent-child observation.^{14,24} In these studies, the parent self-report findings have consistently agreed with other methods of measuring parent and child outcomes. For this reason, the source of parenting and child outcome data for this study will be parent self-report alone.

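### The Census reference for the Aim 3 representativeness profile is not limited to families with young children, so a difference from it, or no difference, cannot be put down to recruitment.

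*Combined protocol and SAP*

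**What the plan says.** The Study Design section fixes who can be enrolled: "Parents ($n = 312$) of 2- to 5-year-old children will be recruited from 4 primary care practices".

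The Analytic plan for Aim 3 builds a demographic, income and technology profile of the enrolled parents. For the demographic and income parts it states "We will use contingency table analyses and independent *t* tests", and the purpose of these tests is to "compare the demographic and income profiles to the characteristics of the population of the primary care sites service catchment communities", with the U.S. Census as the source of the comparator. From this the plan will "assess the extent to which we are either over- or under-representing our priority populations (low-income families) from the local catchment area in this study".

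Table 5 describes Reach as "Proportion and characteristics of parents from the practices that were introduced to and enrolled in the study". Its counts come from the EHR: well-child visits for children aged 2 to 5, parents introduced, and parents not introduced with the reason. The number enrolled is also recorded. Characteristics are listed for enrolled parents only, so no profile of eligible families who did not enrol is planned.

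No section restricts, stratifies or standardises the Census reference to parents or to households with young children.

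**The concern.** The enrolled group and the reference group differ by design. One consists only of parents of young children attending four practices. The other, as written, is the population of the surrounding communities. Age and household structure, both named under Control variables as part of the demographic inventory, depend directly on being the parent of a young child. Income may also differ between such families and the general population.

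A gap between enrollees and the Census figure can thus come from having a young child, from attending these practices, or from who was recruited. The planned tests cannot separate these. The contingency tables and the t tests share the problem, because it lies in the reference and not in the test.

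At stake is the plan's statement on whether the study reached its priority population. A representative sample could be reported as over-representing low-income families, or a real shortfall could go unseen.

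**Working it through.** The plan states no significance level, Census value or low-income share for this comparison, so there is no figure of its own to reproduce. What follows is an illustration.

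**Inputs from the documents:** 312 parents and 4 practices (Study Design).

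**Assumptions:** two-sided 5% level; equal sites, so 312 / 4 = 78 per site; 40% of catchment families with young children are low-income; the general catchment share p0 is 25%, 30% or 35%; the reference value has negligible sampling error.

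**Formula:** z = (p − p0) / √(p0(1 − p0)/n), where p is the share among enrollees.

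**1. Recruitment exactly representative (p = 0.40), tested against the general population**

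| p0 | n = 312 | n = 78 |
|---|---|---|
| 0.25 | 0.15/0.0245 = 6.12, p < 0.0001 | 0.15/0.0490 = 3.06, p = 0.002 |
| 0.30 | 0.10/0.0259 = 3.85, p = 0.0001 | 0.10/0.0519 = 1.93, p = 0.054 |
| 0.35 | 0.05/0.0270 = 1.85, p = 0.06 | 0.05/0.0540 = 0.93, p = 0.35 |

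Against the correct 40% reference, z = 0 in every row.

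**2. How often a representative sample would be flagged.** Let the general share be 20%, 30% or 40%, and let the family share exceed it by a fixed gap. The probability of a significant result at n = 312 is:

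- no gap: 0.05
- 2 points: 0.15, 0.13, 0.11
- 5 points: 0.59, 0.49, 0.44
- 10 points: 0.98, 0.96, 0.95

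At one site of 78, a 10-point gap gives 0.59, 0.49 and 0.44.

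**3. Masking.** Let families be 40% low-income, the general population 30%, and enrollees 30%. Enrolment then falls 10 points short of the families it should represent.

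- Against families, n = 312: −0.10/√(0.40 × 0.60/312) = −0.10/0.0277 = −3.61, p = 0.0003. If the true enrolled share is 30%, detection probability is 0.96.
- Against the general population: z = 0, and detection probability is 0.05.
- At one site, even the correct reference gives −0.10/0.0555 = −1.80, p = 0.07. Masking therefore matters mainly for the pooled comparison.

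**4. Precision.** The 95% half-width at p = 0.40 is 1.96 × √(0.24/312) = 0.054 pooled and 1.96 × √(0.24/78) = 0.109 per site.

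**The case against.** The strongest reply is that the plan names no Census table. It speaks of the communities' population and then of low-income families, so the analysts may intend a family-level tabulation. On that view this is missing detail and not a wrong choice. It is true that the text never says households without young children are to be included. But no restriction is stated, and followed as written the comparison uses the general population.

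The second reply is about size. Every share above is assumed. The RE-AIM descriptives are planned for each site, and at about 78 parents the 40% against 30% case just misses significance. This stands, and it limits the point: the pooled comparison is exposed to moderate gaps, single sites mainly to larger ones.

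The third is about scope. Comparing enrollees with the wider community is a legitimate descriptive question. That also stands, provided the result is not read as evidence about recruitment.

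A reader might infer more than the documents support:

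- **That the whole Reach conclusion is compromised.** It is not. The introduced and enrolled proportions rest on counts that do not use the Census, and the cascade model uses none of this comparison.
- **That the test will be significant in the wrong direction.** The first example shows a false positive under exact representation, not a reversed sign. The documents give no shares from which a direction could be derived.
- **That the independent t test is itself a material error because a Census value is fixed.** No effect on the conclusion has been shown, and a restricted Census estimate can carry sampling error of its own.

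**Conclusion.** The point holds in limited form. The Aim 3 profile compares parents of 2- to 5-year-olds with a reference not restricted to families like theirs, then draws a conclusion about representation of low-income families. Neither a difference nor its absence can be attributed to recruitment.

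The distortion depends entirely on how far low-income shares differ between families with young children and the general catchment population, which the documents do not say. If they do not differ, income is unaffected, though age and household structure may still be. With a 5-point gap, a representative pooled sample would be flagged about half the time; with 10 points, nearly always.

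The effect is confined to the representativeness profile within Reach. Aims 1 and 2 are untouched. The change should be made because the comparator as written can mislead and is cheap to correct.

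**What to change.** In the Aim 3 analytic plan:

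1. Name as the reference the Census tabulation for catchment families or households with young children, in the closest available age band.
2. Report the enrollee-minus-reference difference with a 95% confidence interval, pooled and per site. Include the Census estimate's published sampling error where it is not negligible.
3. Keep the general-population comparison, if wanted, as description only, with no inference about recruitment.

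A comparison with eligible families who did not enrol would be more direct, but it should be optional. The documents do not show that the EHR holds income or household fields for those families, so it applies only if the fields already exist and their use is permitted.

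The cost is a change of SAP wording and a different Census table, with no new data from participants. The downside is that restricted tabulations are less precise and may not match ages 2 to 5 exactly. Attendance at these practices also remains mixed into any catchment comparison, and the report should say so.
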